2.2.4 Area Under Curve (AUC)

AUC will be estimated as the area under the ROC curve. To construct a ROC curve, the specificity on the x-axis and sensitivity on the y-axis will be plotted. (Šimundić, 2009 Jan) Sensitivity and specificity are calculated at various values of VFR and FFR, and the AUC curve will be drawn using logistic regression.

The point estimate and 95% confidence interval for this statistic will be reported.

2.3 Endpoint Analysis

All endpoint analyses are diagnostic measures intended to evaluate the performance of the VFR algorithm versus the gold standard, FFR.

Statistical Analysis Plan

2.3.1 Diagnostic Definitions

2.3.1.1 FFR Definition of Disease State

FFR with a binary cut-off of 0.80 will be used as the reference standard for comparison, and an FFR value ≤ 0.80 will be considered positive (ischemia-causing) and an FFR value > 0.80 will be considered negative (non-ischemia-causing).

2.3.1.2 VFR Definition of Disease State

VFR with a binary cut-off of 0.80 will be used as the reference standard for comparison, and a VFR value ≤ 0.80 will be considered positive (ischemia-causing) and a VFR value > 0.80 will be considered negative (non-ischemia-causing).

2.3.1.3 Diagnostic Definitions

The following 2x2 table provides diagnostic definitions of true positive (TP), false positive (FP), true negative (TN) and false negative (FN) within the context of this study.

	FFR ≤ 0.80	FFR > 0.80
VFR ≤ 0.80	True Positive (TP)	False Positive (FP)
VFR > 0.80	False Negative (FN)	True Negative (TN)

The following sections contain these diagnostic definitions of TP, TP, FN, and TN to explain how to calculate the endpoint data.

2.3.2 Co-Primary Endpoints

The co-primary endpoints of the study will be the sensitivity and specificity of VFR against FFR, each of which will be tested against a prespecified performance goal. These two endpoints will be described further in the following sections.

2.3.2.1 Co-Primary Endpoint: Overall Sensitivity

The first co-primary endpoint is the overall sensitivity of VFR against FFR.

2.3.2.1.1 Hypothesis

Let $\text{Sens}(\text{VFR})$ be the overall sensitivity of VFR, while PG_{sens} is the performance goal for this primary endpoint. The following hypothesis will be tested:

$$H_0: \text{Sens}(\text{VFR}) \leq \text{PG}_{\text{sens}}$$

$$H_1: \text{Sens}(\text{VFR}) > \text{PG}_{\text{sens}},$$

2.3.2.1.2 Analysis Method

This confidential document is the property of Abbott and shall not be reproduced, distributed, disclosed or used without the express written consent of Abbott.

Statistical Analysis Plan

The overall sensitivity of the hybrid approach will be estimated using the 2×2 contingency table comparing VFR and FFR measurements. Sensitivity is defined as the proportion of VFR positive lesions (Šimundić, 2009 Jan) in the group of FFR positive lesions, which can be expressed in the following way:

$$Sensitivity = \frac{TP}{TP + FN}$$

Where TP denotes the number of True Positives (both VFR and FFR positive) and FN denotes the number of False Negatives (VFR negative but FFR positive).

2.3.2.2 Co-Primary Endpoint: Overall Specificity

The second co-primary endpoint is the overall specificity of VFR against FFR.

2.3.2.2.1 Hypothesis

Let $Spec(VFR)$ be the overall specificity of VFR, while PG_{spec} is the performance goal for this primary endpoint. The following hypothesis will be tested:

$$\begin{aligned} H_0: Spec(VFR) &\leq PG_{spec} \\ H_1: Spec(VFR) &> PG_{spec}, \end{aligned}$$

2.3.2.2.2 Analysis Method

The overall specificity will be estimated using the 2×2 contingency table comparing VFR and FFR measurements. Specificity is defined as the proportion of VFR negative lesions in the group of FFR negative lesions (Šimundić, 2009 Jan), which can be expressed in the following way:

$$Specificity = \frac{TN}{TN + FP}$$

Where TN denotes the number of True Negatives (both VFR and FFR negatives) and FP denotes the number of False Positives (VFR positive but FFR negative).

2.3.3 Secondary Endpoints

All secondary endpoints will be summarized descriptively on the primary analysis population. No hypothesis testing will be performed for these endpoints.

This confidential document is the property of Abbott and shall not be reproduced, distributed, disclosed or used without the express written consent of Abbott.

Statistical Analysis Plan

2.3.3.1 Secondary Endpoint #1: Overall Diagnostic Accuracy

The overall diagnostic accuracy will be estimated using the 2×2 contingency table comparing VFR and FFR measurements. Overall diagnostic accuracy is defined as the proportion of correctly classified lesions among all lesions (Šimundić, 2009 Jan), which can be expressed in the following way using definitions from Section 2.3.1.3:

$$\text{Overall Diagnostic Accuracy} = \frac{TP + TN}{TP + TN + FP + FN}$$

Where TP denotes the number of True Positives, TN denotes the number of False Negatives, TN denotes the number of True Negatives, and FN denotes the number of False Negatives.

The point estimate and 95% confidence interval for this statistic will be reported.

2.3.3.2 Secondary Endpoint #2: Positive Predictive Value (PPV)

PPV will be estimated using the 2×2 contingency table comparing VFR and FFR measurements. PPV is defined as the proportion of lesions with the disease and with a positive test result among the group of lesions with a positive test result (Šimundić, 2009 Jan), which can be expressed in the following way using definitions from Section 2.3.1.3:

$$PPV = \frac{TP}{TP + FP}$$

Where TP denotes the number of True Positives and FP denotes the number of False Positives.

The point estimate and 95% confidence interval for this statistic will be reported.

2.3.3.3 Secondary Endpoint #3: Negative Predictive Values (NPV)

NPV will be estimated using the 2×2 contingency table comparing VFR and FFR measurements. NPV is defined as the proportion of lesions without the disease and with a negative test result among the group of lesions with negative test results (Šimundić, 2009 Jan), which can be expressed in the following way using definitions from Section 2.3.1.3:

$$NPV = \frac{TN}{TN + FN}$$

Where TN denotes the number of True Negatives and FN denotes the number of False Negatives.

The point estimate and 95% confidence interval for this statistic will be reported.

2.3.3.4 Secondary Endpoint #4: Correlation between VFR and FFR

The correlation between VFR and FFR will be estimated at the lesion level as the R^2 correlation coefficient from the simple linear regression model using VFR value as the independent variable and FFR as the dependent variable.

This confidential document is the property of Abbott and shall not be reproduced, distributed, disclosed or used without the express written consent of Abbott.

Statistical Analysis Plan

2335

2.4

Statistical Analysis Plan

2.5 Interim Analysis

No formal interim analyses are planned for this study. As such, no formal statistical rule for early termination of the trial is defined.

[figure not shown]
2.6 Timing of Analysis

The primary endpoint analysis will be conducted after at least 310 subjects have undergone a procedure and usable VFR and FFR readings have been obtained.

2.7 Study/Trial Success

The clinical investigation will be deemed a success if both primary endpoint hypotheses are rejected at the 0.025 level.

2.8 Subgroups for Analysis

2.9 Handling of Missing Data

Every effort will be taken to obtain complete data for all subjects. Any subject without a pair of qualified FFR and VFR measurements will be excluded from analysis.

Statistical Analysis Plan

2.10 Poolability Issue

14

14 

— *f*

11. **What is the primary purpose of the *Journal of Clinical Endocrinology and Metabolism*?**

11

2.11 Multiplicity Issues

Since the endpoints are co-primary and both must be passed to declare study success, there is no need for multiple comparison adjustment.

2.12 Adjustments for Covariates

Unless otherwise specified, no adjustments for covariates will be made for any of the variables in the analyses.

2.13 Sensitivity Analysis

Generalized linear models may be utilized to adjust for within-subject correlation.

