## 6.2 PCI Procedure

The following is a description of the image acquisition and treatment steps to be used during the index procedure. The pre-PCI procedures should be conducted in the following order: Pd/Pa and RFR snapshot measurement, FFR measurement, dedicated period for resolution of hyperemia, RFR pullback measurement, drift check, and OCT imaging procedure. The optional post-PCI step should include final OCT imaging procedure, followed by physiological measurements (refer to the flowchart in **Figure 2**). Post-PCI study data collection step is optional but strongly recommended if PCI is performed.

All OCT data and physiological indices measurements will be stored digitally for subsequent analysis and these images must be sent to the Core Laboratory for quality check.

Any vessel preparation (if necessary) with balloon dilation or atherectomy should be performed only after pre-PCI physiological indices measurement and OCT have been performed.

If applicable, PCI will be performed according to local standard practice. PCI information will be collected on the appropriate eCRF. For each treated lesion, the guiding catheter size, the total number of stents used, and the relevant stent information (diameter and length) must be recorded on the appropriate eCRF. Any vessel preparation step including, pre-dilation, post-dilation, or atherectomy device use must also be recorded. If the subject undergoes atherectomy during PCI, post-PCI OCT and physiological steps are not needed and that is the end of the protocol for the subject.

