### 6.2.1 Physiological indices measurement procedures

In all cases, physiological indices measurement must be performed. Any standard guidewire must be removed completely from target vessel prior to any physiological measurement.

At least 100 µg IC nitroglycerin must be administered prior to physiological assessment. The preparation and use of the PressureWire will be according to its respective IFU. The aortic pressure transducer and PressureWire must both be equilibrated to zero pressure outside of the body. The PressureWire is then advanced to the aorto-ostial junction where PressureWire equalization is performed after ensuring the presence of an appropriate aortic waveform (distinct dicrotic notch), with guide disengagement performed, if necessary. PressureWire is then advanced across the lesions with the sensor positioned into the distal coronary artery and at least 10 mm distal to the most distal target lesion. The PressureWire position is then captured via cine documentation with contrast administration (this may be successfully

*This confidential document is the property of Abbott and shall not be reproduced, distributed, disclosed or used without the express written consent of Abbott*

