### 6.2.2 OCT procedures

The preparation and use of the OCT catheter will be according to its respective IFU. For all indicated vessels, if less than 10 minutes have passed since the last dose of IC nitroglycerine, no extra dose is needed. If more than 10 minutes have passed since the last dose of IC nitroglycerine, at least 100 µg IC nitroglycerin should be re-administered before OCT pullbacks. The proximal and distal reference segments are initially identified by angiography. The proximal and distal reference diameters should be recorded on the eCRF. OCT Imaging must be performed using the pullback device at 75 mm pullback (survey mode), 5 frames per mm over 2.1 seconds. The OCT catheter should be placed at the location where the imaging lens is at the same location as the PressureWire sensor and would reach the guide catheter at the end of the imaging run as well as at least 10 mm distal to the distal end of the lesion, with the aim of imaging as much of the coronary artery as possible. All significant lesions in a vessel need to be within a single OCT pullback. OCT pullback image will be qualified as long as all disease segment was captured. The lens position should be captured via cine documentation prior to each pullback. For standard pullback, the recommended contrast injection volume is 14 ml at an injection rate of 4 mL/s in the left coronary artery and 12 mL at an injection rate of 3 mL/s in the right coronary artery. Cine angiography with contrast opacification of the coronary artery in the desired angiographic co-registration view(s) must be performed during the pre- and (optional) post-PCI OCT pullback without panning. Contrast volume and method are collected on the eCRF.

For cases with PCI, the post-PCI study data collection step is optional. If a post-PCI study data collection was performed, both intermediate and final OCT pullbacks should be collected after OCT-guided stent optimization was done, and the post-PCI physiological assessment must be performed after the final OCT run. Pre-PCI, (optional) intermediate post-PCI, and (optional) final post-PCI OCT pullback images need to be uploaded to the OCT Core Laboratory via BioClinica website.

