### 6.2.3 Multiple target lesions/vessels treatment

Subjects requiring multi-vessel PCI may be enrolled in this trial. There is no limit on the number of target lesions per epicardial vessel and target vessels per patient in this study. All target lesions and vessels must satisfy all inclusion and exclusion criteria.

*This confidential document is the property of Abbott and shall not be reproduced, distributed, disclosed or used without the express written consent of Abbott*

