### 6.2.6 Bifurcation lesions consideration

Bifurcation lesions consideration is shown in **Figure 4**.

- **Scenario 1:** For the main branch lesion with a side branch that has a minimal disease which is defined as <40% diameter stenosis by visual estimate), the main branch lesion can be enrolled as the target lesion. Treatment of the side branch is optional and outside of the study protocol.
- **Scenarios 2 and 3:** If the side branch vessel has significant ostial disease with a planned single (**Scenario 2**) or two-stent (**Scenario 3**) strategy, only the main vessel can be enrolled into the study, following the FUSION workflow in the main branch. For two-stent strategy, this will count as one lesion and physiology measurement and OCT imaging are not required in the side branch. Treatment of the side branch will be outside of the study protocol.
- **Scenario 4:** For the main branch and side branch lesions that are both to be considered as target lesions, these two lesions need to be distant from each other (i.e., side branch lesion is not ostial) treated independently and both branches are of adequate size to undergo physiology and OCT measurements. In that setting, the main and the side branch are considered separate target vessels and all physiology and OCT. The measurements of both physiology and OCT must be done in the respective target vessel separately. i.e., in the side branch for the side branch lesion assessment. Of note, while assessing side branch lesions, upstream lesions in the main branch must also be imaged.

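### Sensitivity and specificity count lesions although FFR and OCT are read per vessel, and the only readable allowance for within-subject correlation is an optional sensitivity model

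*SAP*

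**What the plan says.** **Counting unit.** SAP 2.3.2.1.2: "Sensitivity is defined as the proportion of VFR positive lesions", taken among the FFR-positive lesions. SAP 2.3.2.2.2: "Specificity is defined as the proportion of VFR negative lesions in the group of FFR negative lesions". Protocol 8.2.1.1.2 and 8.2.1.2.2 agree. SAP 2.3.3.4 also places the VFR-FFR correlation at lesion level. The analysis population (SAP 2.1.1) and the analysis trigger (SAP 2.6) are stated in subjects.

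**Measurement unit.** Protocol 6.2.1 puts the pressure sensor "at least 10 mm distal to the most distal target lesion". Protocol 6.2.2 adds: "All significant lesions in a vessel need to be within a single OCT pullback". Each time point therefore gives one FFR reading and one pullback per vessel.

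**Rows per patient.** Protocol 6.2.3: "There is no limit on the number of target lesions per epicardial vessel and target vessels per patient in this study". Protocol 6.2.6 settles bifurcations only. "For two-stent strategy, this will count as one lesion", and a main branch and side branch with independent lesions are separate target vessels, each measured separately. For two target lesions in one vessel, no readable rule says whether they give one row or two.

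**Post-PCI readings.** Protocol 6.2: "Post-PCI study data collection step is optional but strongly recommended if PCI is performed". Protocol 6.6 covers pre- and post-PCI data and sends all acceptable recordings to endpoint analysis. No readable rule restricts the co-primary table to pre-PCI pairs.

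**Correlation and success.** SAP 2.13 is the only readable mention of within-subject correlation: "Generalized linear models may be utilized to adjust for within-subject correlation". Success requires both primary hypotheses to be rejected at 0.025 (SAP 2.7).

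**The concern.** Two rows from one patient in the same FFR stratum are unlikely to be independent. If the same vessel pair is entered for two lesions, they are identical. A binomial bound that treats such rows as independent is too narrow. The adjustment is listed under sensitivity analysis, which suggests that the primary bound does not make it. A generalized linear model by itself does not correct for clustering; it needs robust variance from estimating equations, or random effects, and SAP 2.13 names neither. What is at stake is the 0.025 error rate for whichever co-primary endpoint is decisive.

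**Working it through.** **What cannot be reproduced.** The inputs to N = 310 (goals, expected performance, FFR-positive share, power) are not readable, so the planned sample size was not recomputed. The documents give neither the share of patients with several rows nor a correlation. All values below except the 0.025 level are assumptions.

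**Set-up.** In one FFR stratum, a share f of patients gives two rows and the rest give one. With success probability p at the goal and within-pair correlation rho, the pair probabilities are P(both correct) = p² + rho·p(1−p) and P(both wrong) = (1−p)² + rho·p(1−p). A rho of 1 means one vessel pair is counted twice. The assumed test is an exact one-sided binomial test at 0.025 on all rows. Exact Clopper-Pearson is the only interval method named in the readable SAP (2.2.2), where it is optional and descriptive.

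**One cell worked through.** Take 150 patients, p = 0.80 and f = 0.20. This gives 120 + 2×30 = 180 rows, and the test rejects at 155 or more correct. The rejection probability is 0.0217 at rho 0, 0.0270 at 0.3, 0.0325 at 0.6 and 0.0403 at 1.

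**Mean error by enumeration** (even numbers of patients from 100 to 200; goals 0.70, 0.75, 0.80, 0.85):

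| rho | f=0 | f=0.02 | f=0.05 | f=0.10 | f=0.20 | f=0.30 | highest cell at f=0.30 |
|---|---|---|---|---|---|---|---|
| 0.3 | 0.0192 | 0.0199 | 0.0207 | 0.0223 | 0.0249 | 0.0269 | 0.0330 |
| 0.6 | 0.0192 | 0.0204 | 0.0221 | 0.0250 | 0.0302 | 0.0344 | 0.0415 |
| 1.0 | 0.0192 | 0.0212 | 0.0240 | 0.0288 | 0.0376 | 0.0448 | 0.0531 |

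The exact test starts below 0.025 because it is discrete, and that margin absorbs mild clustering. Within this grid, mean error exceeds 0.035 only when one vessel result is counted twice in about 20% of patients or more.

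**Normal approximation as a cross-check.** The design effect is DE = 1 + [2f/(1+f)]·rho, and the error is P(Z > 1.96/√DE).
- f = 0.10, rho = 0.3: DE = 1 + 0.1818×0.3 = 1.0545; error 0.0282.
- f = 0.30, rho = 1: DE = 1.4615; error 0.0525.

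**From f to two-vessel patients.** Suppose half of vessels are FFR-positive, a share q of patients has two measured vessels, and the two agree in FFR status with probability c. Then f = qc/[1 + q(1−c)]. For f from 0.10 to 0.30, q runs from 22% to 86% at c = 0.5, from 15% to 49% at c = 0.7, and from 10% to 30% at c = 1.

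**Joint requirement.** With both endpoints at their goals and the two strata treated as independent, even the largest mean error gives 0.0448² = 0.002. The inflation counts only when one endpoint is at its goal and the other passes almost surely.

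**The case against.** The strongest reply is that the decisive text is out of sight. The primary hypothesis text is redacted or breaks off, the sample-size section is unreadable, and a lower confidence bound sits in both abbreviation lists without being used in readable text. SAP 2.8 and 2.10 and the end of 2.3.3 are also largely lost. A clustered bound or a row rule could be there. This stands, and it limits the conclusion to the readable text.

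Three stronger readings are tempting, and the documents support none of them.

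- *The primary test ignores clustering.* The placement in SAP 2.13 implies this but does not prove it.
- *One vessel reading is entered once per lesion.* No passage says so. SAP 2.9 speaks of a subject's pair of qualified measurements, and the word lesion in the endpoint definitions follows a cited paper on basic definitions. The unit is unclear; duplicate rows are not shown.
- *Post-PCI pairs are pooled and inflate the error.* Protocol 6.6 is a general core-laboratory statement, while enrollment (Protocol 6.2.5) and FFR monitoring (SAP 1.6) rest on pre-PCI or baseline data. Adding 20 FFR-negative post-PCI rows with specificity 0.95 to 120-190 pre-PCI rows at a goal of 0.75 or 0.80 would move mean rejection from 0.020 to 0.075. That number and that specificity are assumed, and the result is an error only if the target is pre-PCI specificity. This is a question of estimand and is not evidence of clustering.

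It is also fair that distinct vessels at correlation 0.3 leave mean error at or below 0.027. The revision history describes the N = 310 calculation as assuming no dual vessels, so few two-vessel patients may have been expected.

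**Conclusion.** The concern holds for the readable text, as a cheap improvement and not as a demonstrated failure of error control. The counting unit does not match the measurement unit, and the only readable correction for correlation is optional and cannot alter the success decision. If the primary bound is an unadjusted exact bound, the effect is negligible with 2-5% of patients paired, small for distinct vessels at correlation 0.3, and up to 0.034 on average at 0.6. It reaches 0.045 only if single vessel results are counted twice in 30% of patients. These figures rest on the assumed pairing share, correlation, stratum size, goals and test.

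**What to change.** Make both changes by documented amendment (Protocol 8.12) before Group 2 is unblinded to VFR (Protocol 3.2.1, SAP 1.6).

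1. Make the primary lower bounds for sensitivity and specificity clustered by subject, for example logistic GEE with robust variance, and compare them with the performance goals. Move the unadjusted binomial bound to SAP 2.13 as the sensitivity analysis.
2. Unless the unreadable text already does so, state in Protocol 8.2 and SAP 2.3 that each target vessel's pre-PCI VFR-FFR pair enters the co-primary 2x2 table once. Report optional post-PCI pairs separately.

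**Cost.** If lesions were meant as separate rows, the row count falls. Standard errors grow by √DE − 1: from 1.4% (f = 0.05, rho = 0.3; DE = 1.0286) to 13.0% (f = 0.30, rho = 0.6; DE = 1.2769).

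A simulation (120-180 patients, goals 0.75 and 0.80, 20,000 runs per cell) gave the GEE bound a mean error of 0.0202-0.0230 for f up to 0.30 and rho up to 1. Power with the true value 0.10 above the goal, exact binomial versus GEE, was:
- 0.873 versus 0.877 with no pairs;
- 0.916 versus 0.902 at f = 0.20, rho = 0.3;
- 0.923 versus 0.879 at f = 0.30, rho = 0.6, where the exact test's mean error in the enumeration above is already 0.034.

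If 310 was indeed sized without dual vessels, planned power should not depend on the extra rows.
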